1.0 Background

1.1 Head and Neck Cancer

Worldwide, head and neck cancers affect more than 550,000 individuals annually with men accounting for up to two-thirds of reported cases [1]. The relative prevalence of head and neck cancers can be attributed to the regional variation of risk factors such as tobacco use, alcohol consumption and infection from human papillomavirus (HPV) or Epstein-Barr Virus (EBV)[1-4]. Within the United States, nearly 4% or about 42,000 cases of all malignancies can be attributed to cancer of the oral cavity and nasopharynx [5]. Treatment for patients with head and neck carcinomas generally include single modal therapy such as chemotherapy or radiation therapy or treatment with multimodal therapy such as induction therapy with concurrent Chemoradiotherapy[6-11]. Treatment is associated with numerous and often severe toxicities.

1.2 Mucositis

Oral mucositis, ulceration of the oral mucosa, is one of the major and frequent complications of radiation and chemotherapy in head and neck cancer patients[12, 13]. A combination of dose-related chemoradiation epithelial damage, micro-vascular injury, elevated release of cytokines such as TNF- α , and oxidative stress with subsequent generation of reactive oxygen species contribute to the development of oral mucositis[12, 14]. Recent data suggests that occurrence of severe oral mucositis occurs in up to 66-85% of patient's [15, 16]. Development of mucositis is accompanied with severe pain [13, 17]. Mucositis associated pain has a mixed pathogenesis which includes both somatic and neuropathic components. The pain symptoms usually begin two to three weeks after the start of chemoradiation therapy and are at its worst at the completion of therapy. Development of mucositis in cancer patients has significant impacts on health, quality of life, and recovery [14, 17]. Associated pain results in dysphagia making it difficult for patients to eat and thus increasing their risk for weight loss and volume contraction dehydration throughout therapy as well precipitates the need for parenteral nutrition[12, 18]. Furthermore, erosive mucositis puts patients at risk for development of secondary infection and sepsis especially in the presence of concurrent neutropenia [14]. Severe mucositis may require a dose reduction during therapy, altering the course of Chemoradiotherapy originally set forth.

Current treatment of mucositis includes symptom management with routine oral care, mucosal coating agents, chlorhexidine, both topical and systemic analgesics, and oral cryotherapy[15, 16, 18]. Systemic analgesics commonly used for treatment include opioids, non-steroidal anti-inflammatory agents, and acetaminophen[15]. Because of issues with dysphagia, oral administration of analgesics may be hampered. Thus, transdermal formulations are frequently utilized. Unfortunately, opioids are associated with well-documented side effects (e.g. addiction, tolerance, and dependence) and are frequently ineffective for controlling mucositis associated pain [19]. Thus, a search for other pain medications to manage mucositis induced pain is of clinical importance. Since peripheral sensitization is one of the underlying

mechanisms for mucositis associated pain, it may be hypothesized that agents that are effective for neuropathic pain may modulate mucositis associated pain[17, 20]

1.3 Pain

It is estimated that pain affects more than 20% of adults around the world making it one of the most common patient complaints[21]. Pain is often subdivided into two categories – acute and chronic. Acute pain is believed to be an evolutionarily protective mechanism designed to protect the body from harmful stimuli and situations (ie rapidly moving one’s hand from the burning stove). Thus acute pain is the body’s defense system that produces reflexive actions to prevent severe tissue injury and allow time for healing. Chronic pain is defined as that which lasts beyond the ordinary duration of time that an insult or injury to the body needs to heal. Unlike acute pain, which has a biological role, chronic pain is a pathological process that causes severe impairment even when the insult or injury has healed.

Two types of pain pathways that have been a target of pharmacological therapy include neuropathic pain and nociceptive pain. Neuropathic pain results from a lesion or disease of the nervous system that causes abnormal neural activity in the neural pathways that signal pain[22]. Patients with neuropathic pain often describe sensations of “burning,” “pins and needles,” or “electrical stabbing pains.” Etiologies of neuropathic pain fall under four broad categories: (1) focal or multifocal lesions of the peripheral nervous system such as entrapment syndromes, postherpetic neuralgia, or diabetic mononeuropathy; (2) polyneuropathies such as vitamin deficiencies, HIV neuropathy, and hypothyroidism; (3) central nervous system lesions such as multiple sclerosis, thalamic infarcts, and syringomyelia; (4) complex neuropathic disorders such as complex regional pain syndromes (reflex sympathetic dystrophy and causalgia).[22]

Alternatively, the nociceptive pain pathway detects noxious mechanical, thermal and chemical stimuli through their specialized free nerve endings (nociceptors) found in the skin, visceral organs, articular surfaces and periosteal surfaces [23]. Receptors responsible for the transduction of nociceptive signals include the Vanilloid Receptor (VR-1) and the Vanilloid-Like Receptor (VRL-1) [24]. Both of these receptors belong to the larger family of transient receptor potential (TRP) channels that resemble voltage-gated ion channels. Once the nociceptors are stimulated, afferent signals travel via the spinothalamic tracts to the brain synapsing in the sensory cortex where the pain signals are processed. Recent research suggests that there are parallel pain pathways that project to secondary brain regions such as the amygdala, hypothalamus, and reticular formation that regulate the sensory discriminative aspects of pain (location, quality, and quantity of the pain) as well as the affective-motivational aspects of pain that are responsible for evoking fear, anxiety, and activation of the autonomic nervous system (the flight or fight response)[25-29]. Thus pain is a full perceptual experience that involves multiple sensory modalities that results in a constellation of systemic symptoms ranging from changes in mood, cognition dysfunction, as well as neurovegetative and somatic complaints.

There are two mechanisms that are thought to facilitate persistent chronic pain and hyperalgesia – peripheral sensitization and central sensitization. Peripheral sensitization is thought to result from the interaction of nociceptors and the “inflammatory soup” of molecules from the injured or inflamed tissue. The release of bradykinin, cytokines, histamine, prostaglandins, growth factors, and extracellular protons create a chemical environment that interacts with nociceptors and pain nerve fibers, augmenting their response to stimuli. Thus

slightly painful stimuli and or otherwise non-painful stimuli are perceived as significantly more painful. Peripheral sensitization explains why medications such as non-steroidal anti-inflammatory drugs (NSAIDs) and anti-histamines that inhibit the production of prostaglandins and histamine respectively are effective in managing pain. [30]

Central sensitization results from an activity-dependent increase in the excitability of dorsal horn neurons of the spinal cord following repeated stimulation from nociceptive afferent signals. Following repeated stimulation, transcriptional changes of ionotropic NMDA receptors in the dorsal horn cells results in removal of the normal voltage-dependent magnesium ion block, increasing the time the channel is open. This is thought to increase the excitability of the dorsal horn cell. Thus, nociceptive afferents that would otherwise be subthreshold become sufficient to depolarize the dorsal horn neurons of the spinal cord pain pathways. Unlike peripheral sensitization, which is restricted to the site of tissue injury, the effects of central sensitization generalize to other inputs that arise from low-threshold mechanoreceptors. Under normal circumstances, these states of heightened pain response return to normal once the insult is removed and tissue healing is complete. [31] However in many pathological pain syndromes, these thresholds are never restored and previously innocuous stimuli result in symptoms of allodynia and hyperalgesia that can spread beyond the site of injury.

1.4 Gabapentin

Gabapentin is a drug structurally similar to GABA that interacts with voltage calcium channels located throughout cortical brain tissue[32, 33]. Although labeled for treatment of partial seizures, Gabapentin's unlabeled indications include treatment of neuropathic pain conditions such as restless leg syndrome, diabetic neuropathy, fibromyalgia and migraines [33-35]. The question has been raised as to whether Gabapentin can decrease radiation-induced acute and chronic oral mucositis pain in head and neck cancer patients. The majority of data looking at Gabapentin in management of acute and chronic pain has taken been done in the setting of post-operative management. A review of Gabapentin in the treatment of acute post-operative pain by Chang et al found that the administration of gabapentin was associated with post-operative reductions of (1) rescue analgesics and pain scores in patients undergoing coronary artery bypass graft, (2) the requirements of antiemetics in patients undergoing neurological surgery and hysterectomy, and (3) a reduction in pain and narcotic use in patients undergoing lumbar spinal surgery at every time point [36]. A second study by Straube et al found that single 250 mg dose of Gabapentin was associated with 50% reduction in acute pain over 6 hours post-operatively (RB of 2.5 with 95% CI 1.2 to 5.0) in 15% of patients vs only 5% in controls as well as a decreased usage of rescue medications [37]

A study looking at the effects of Pregabalin, a drug structurally similar to Gabapentin, found that Pregabalin is effective at reducing neuropathic and inflammatory orofacial pain in rat models [38]. Gabapentin has also been found to improve dysphagia in patients with oropharyngeal squamous cell carcinoma (OPSCC). A case report of 10 head and neck cancer patients treated with gabapentin after failing other interventions found that three 300 mg doses of gabapentin daily eliminated neuropathic pain in 8 of the 10 patients with partial relief of symptoms in the remaining 2 [39]. A study by Starmer et al found that prophylactic treatment of Gabapentin in patients with OPSCC was associated with delayed onset of PEG use (3.7 vs 2.29 week; P=0.013) and earlier removal of their PEG tubes (7.29 vs 32.56 weeks; P=0.039) than controls [40]. Thus it is plausible that treatment of oral mucositis with Gabapentin can be

hypothesized to improve not only pain but also improve quality of life parameters such as swallowing and nutritional intake.

A retrospective study evaluated this question. Investigators conducted a chart review of 42 patients with head and neck malignancies treated with concurrent chemoradiotherapy using an intensity-modulated radiotherapy technique. Pain outcomes for patients treated with gabapentin for prevention of mucositis associated pain were compared to pain outcomes for patients using standard supportive care. Results found that preventive administration of gabapentin reduced overall pain levels and the total dose of opioids utilized [34]. Although the data is intriguing, there are numerous limitations to this study. First, the study was retrospective. Second, patients were not randomized and third, outcomes were not pre-established. None-the-less, the data would support further investigation of gabapentin as chronic preventive measures for mucositis associated pain in patients undergoing chemoradiation for head and neck cancer

1.6 Study Summary:

The overall goal of this study is to determine whether or not Gabapentin can reduce mucositis associated pain in head and neck cancer patients undergoing chemoradiation. Patients seen in the Oncology Clinic for routine surveillance will be informed about the study and asked if they interested in participation. Interested patients will be asked to sign an informed consent. They will then be randomized into to two arms—standard of care and standard of care plus gabapentin. Prior to chemoradiation therapy, subjects will undergo education on chemoradiation as well as foundations of oral care. Subjects will be asked to complete a demographic survey, the Head and Neck Symptom Survey 2.0 plus the General Symptom Survey (VHNSS v2.0 plus GSS), the Profile of Mood States – short form (POMS-SF), the Neurotoxicity Rating Scale (NRS), the and a Quality of Life (QOL) assessment as outlined below. Subjects will also be requested to maintain a pain diary that will be used throughout the study to assess their pain and their mucositis will be graded weekly during their visits.

Upon completion of therapy, the data will be collected and stored in a secure password protected database and the patient's study participation will end. We anticipate the study duration to be 2 years.

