4.0 Enrollment/Randomization

A total of 150 patients planned for primary and adjuvant radiation with or without chemotherapy will be recruited. These patients will be identified in the Vanderbilt Oncology Clinic and at head and neck tumor board. Study staff will approach patients to discuss the study and the possibility of patient participation therein. The objectives and requirements of the study will be described to the patients and any questions will be answered. Interested patients will be given consent for to review. If the patient volunteers to participate in the study, the consent will be signed and they will be given a copy for their records. The original copy will be retained in the study files. The patient will be assigned to the usual care or usual care plus gabapentin arm of the study according to the next group assignment specified in the randomization list generated via the use of a computer-generated, permuted block program developed by Co-I [name].

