5.0 Study Procedures

5.1 Chemoradiation:

Chemotherapy and radiation will be instituted per standard of care. There will be no alterations in standard of care as a result of participation in this study. Disease treatment related data will be obtained through chart review after the completion of therapy.

5.2 Study Treatment:

Patients will be randomized to Arm 1 (Usual Care) or Arm 2 – (Usual Care plus Gabapentin).

Arm 1: Usual Care:

Usual care will include the following:

1. Oral health measures including brushing, flossing, and the use of fluoride toothpaste
2. Oral rinsing with baking soda and salt water gargles every 2-3 hours while awake
3. Miracle mouthwash formulated to include topical lidocaine, Benadryl, and Maalox;
4. Nonsteroidal anti-inflammatories around the clock to treat pain and inflammation
5. Opioid analgesics to include a fixed and breakthrough medication.

Patients will undergo an education session at the beginning of treatment to review foundations of oral care and pain management.

Arm 2: Usual Care plus Gabapentin.

Patients will receive all measures for Arm 1 **PLUS** Gabapentin. Gabapentin will be dose escalated using a slow escalation schema to minimize the sedating effects of medication and avoid undue toxicities:

- Week 1: Gabapentin 100 mg PO 3 times a day
- Week 2: Gabapentin 300 mg PO 3 times a day.
- Week 3: Gabapentin 600 mg PO 3 times a day.
- Week 4 onward: Gabapentin 900 mg PO 3 times a day.

The highest tolerated dose of gabapentin will continue throughout treatment. Missed doses, though regrettable, are part of any patient-administered medication and will not be considered deviations for this study as we are studying practical efficacy. After completion of therapy, mucositis is expected to resolve at a variable rate (1 to 3 months post treatment). Gabapentin will be continued until mucositis resolves **and** pain subsides. Patients will be weaned off opioids prior to initiation of gabapentin de-escalation. Once opioids have been weaned, de-escalation of gabapentin will be initiated. Since the rate at which patients can be weaned of pain medications is variable, de-escalation will be managed by the treating physician. Abrupt discontinuation of gabapentin will be discouraged in order to avoid symptoms related to withdrawal.

5.3 Dose Modifications:

Prior to each dose escalation, patients will be assessed for side effects related to gabapentin.

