Prior to initiating therapy, patients will undergo education sessions with study staff. The educational intervention will include a discussion of oral health foundations as well as a discussion of pain management. This education is standardly applied to all VUMC patients undergoing radiation therapy for HNC and will not be otherwise documented. In addition, patients will also be given written material to review. Patient will be given a pain diary and instructed on its use. Baseline pain medication use will be documented. Patients will complete the demographic survey. Patients randomized to gabapentin will be given a prescription for gabapentin with dose escalation as noted in the treatment section. Patients who do not have insurance or who are unable to afford gabapentin will be provided with medication from the indigent pharmacy. All baseline assessments must be done within 4 weeks of starting concurrent chemoradiation.

Weekly On Treatment Visits:

Starting with the initiation of concurrent chemoradiation, patients will be evaluated on a weekly basis. The evaluation will include:

- 1) review of the weekly pain survey
- 2) for patients on gabapentin (Arm 2) --we will review their compliance log and identify any barriers to compliance and strategies to improve their compliance
- 3) adjustment of pain regimen
- 4) completion and review of the Vanderbilt head and neck symptom survey
- 5) mucositis grading.

End-of-Treatment Visit:

Patients will undergo an evaluation at their final radiotherapy visit or within 2 weeks after. This will include the following:

- 1) review of the monthly diary survey
- 2) for patients on gabapentin (Arm 2) --we will review their compliance log and identify any barriers to compliance and strategies to improve their compliance

- 3) adjustment of pain regimen
- 4) completion and review of the Vanderbilt head and neck symptom survey
- 5) mucositis grading.

6.0 Study Measures:

6.1 Mucositis Grading:

Patients will have an oral exam twice a week as part of standard of care. Mucositis will be graded based on the World Health Organization criteria. Mucositis assessments will be done by trained study staff.

6.2 Patient Reported Outcome Measures:

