Appendix I: Studies to be Done:

	Baseline¥	Week 1	Week 2	Week 3	Week 4	Week 5	Week 6 *	Week 7 *	1,2 3 Months post tx
Study Visit	X	X	X	X	X	X	X	X	X
Chemoradiation Teaching	X								
Foundations of Oral Care	X								
Foundations of Pain Management	X								
Randomization	X								
Gabapentin Arm 2 Only		X	X	X	X	X	X	X	X
Mucositis Grading	X	X	X	X	X	X	X	X	X
Demographic Survey	X								
VHNS Version 2.0		X	X	X	X	X	X	X	X
Pain Survey		X	X	X	X	X	X	X	X
Compliance Survey Arm 2 Only		X	X	X	X	X	X	X	X
Neurotoxicity Scale	X						X		X (month 3 only)
POMS	X						X		X (month 3 only)
QOL	X						X		X (month 3 only)

Disease and Treatment Form	X								
----------------------------	---	--	--	--	--	--	--	--	--

‡ All baseline assessments must be done within 4 weeks before starting concurrent chemoradiation.

* Weekly assessments will continue until the completion of chemoradiation which may vary between 5 and 7 weeks.

An End of Treatment Visit will be conducted 2 weeks after Chemoradiation therapy

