Analyses for study aims. Graphical and descriptive statistical summaries will be generated for all study variables. Evaluation of the key outcome variable data distributions (VHNSS mouth pain scores, opioid dose) will inform the required test distribution (e.g., normal, log-normal). Mixed-level general linear modeling will be used to test study hypotheses. Given that patients will have varying VHNSS pain scores prior to beginning radiation, those baseline values will be included as a covariate in the analyses of outcomes [EOT: VHNSS pain scores (H1.1); opioid use (H1.2); weight loss (H2.1); duration of PEG (H2.2); general symptoms (Aim 4)]. Frequency distributions will summarize the safety and tolerability outcomes (Aim 3). All tests of statistical significance will maintain maximum Type I error of 0.05 ($p < 0.05$).

Sample size justification. The proposed sample size was based on typical VHNSS pain score values during/end-of-treatment in prior studies (M=4.5, SD=2.8). A total sample size of 120 patients (60 per arm) who complete the protocol will provide 80% statistical power (2-tailed alpha=0.05) to detect a decrease of 1.5 points on the VHNSS pain scale due to the addition of gabapentin to usual care. Given a change of 2.0 points on the scale is proposed to be clinically meaningful, this slightly larger sample size will provide coverage in the case that our sample values are slightly more variable than those observed in our prior studies. A total sample size of 120 will also enable us to detect correlations as small 0.25(6.3% shared variance) with 80% power and 2-tailed alpha=0.05. We expect clinically meaningful associations to be larger than this value.

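### Nothing requires the baseline pain covariate to be recorded before patients learn their arm, no masking is described, and neither study calendar schedules a baseline VHNSS

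*Combined protocol and SAP*

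**What the plan says.** **Order of steps.** In section 1.6 (Study Summary), signed consent is followed by "They will then be randomized into to two arms". The instruments come afterwards in the text: "Subjects will be asked to complete a demographic survey, the Head and Neck Symptom Survey 2.0 plus the General Symptom Survey", then the mood, neurotoxicity and quality-of-life measures. Section 4.0 also moves from signed consent to allocation: "The patient will be assigned to the usual care or usual care plus gabapentin arm of the study according to the next group assignment". The Baseline part of section 5.6 treats patients as already allocated: "Patients randomized to gabapentin will be given a prescription for gabapentin with dose escalation as noted in the treatment section".

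**Masking.** Arm 1 is usual care. For Arm 2, section 5.2 says "Patients will receive all measures for Arm 1" and adds gabapentin. No placebo or masking is described.

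**Timing rule.** Baseline is tied to chemoradiation, not to allocation. Section 5.6 has "All baseline assessments must be done within 4 weeks of starting concurrent chemoradiation"; both copies of Appendix I have "All baseline assessments must be done within 4 weeks before starting concurrent chemoradiation".

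**Calendar.** Randomisation and the neurotoxicity, mood and quality-of-life measures share one Baseline column, with no order inside it. The VHNSS has no Baseline mark in either copy. Its first mark is Week 1, the column where gabapentin also starts.

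**Use of the baseline.** Section 10.0 notes that pain scores will differ between patients before radiation begins, and states that "those baseline values will be included as a covariate in the analyses of outcomes".

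**The concern.** A baseline covariate is safe to adjust for only if allocation cannot have influenced it. Here both the covariate and the outcome of Hypothesis 1.1 are the patient's own pain ratings, and the patient may know the arm when giving the first of them. Any shift that this knowledge causes is carried into the adjusted treatment effect by the planned model. The resulting baseline difference between arms could not later be told apart from chance imbalance.

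The calendars add a second route. If staff follow them literally, the first VHNSS score is the Week 1 score, taken after allocation and possibly after the first gabapentin doses. The covariate would then either be missing or not be the pre-radiation value that section 10.0 relies on.

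At stake are the two comparisons between arms: pain (Hypothesis 1.1) and, less directly, opioid use (Hypothesis 1.2), which is adjusted for the same baseline.

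**Working it through.** **1. The plan's own figure.** Section 10.0 gives a difference of 1.5, SD 2.8, two-sided alpha 0.05, 60 per arm and 80% power.

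- n per arm = 2 × (1.960 + 0.842)² × (2.8 / 1.5)² = 54.7, so 55 (110 in total).
- At 60 per arm, SE = 2.8 × √(2/60) = 0.511. Then 1.5 / 0.511 - 1.960 = 0.97, which gives 83.5% power.
- 120 / (1 - 0.20) = 150, as stated in section 4.0.

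The plan's size is therefore slightly conservative. The section says it allows for more variable data, and an SD of about 2.93 gives 80% at 60 per arm. None of this depends on the present point.

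**2. Effect of a shifted baseline.** Let X be the baseline that would be reported without knowledge of the arm, A = 1 for gabapentin, b the slope of outcome on baseline, and T the true effect.

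- Outcome: Y = b·X + T·A + error.
- Recorded baseline: X* = X + d·A.
- Substituting: Y = b·X* + (T - b·d)·A + error.

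The adjusted effect is T - b·d, so the bias is -b·d. This is the analysis at a single time point, used as a simplification of the planned mixed model.

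**3. Illustration.** The protocol gives neither b nor d. Assumed ranges are b = 0.3 to 0.7 and d = -0.25 to -1.0 point, plus one case with the opposite sign. T = -1.5, 60 per arm, residual SD = 2.8 × √(1 - b²), which takes the baseline SD as equal to the outcome SD.

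| b | d | Bias | Adjusted effect | Power with shift | Power without shift |
|---|---|---|---|---|---|
| 0.3 | -0.25 | +0.075 | -1.425 | 83.2% | 86.8% |
| 0.3 | -1.0 | +0.30 | -1.20 | 69.2% | 86.8% |
| 0.5 | -0.5 | +0.25 | -1.25 | 80.6% | 92.3% |
| 0.5 | +0.5 | -0.25 | -1.75 | 97.7% | 92.3% |
| 0.7 | -1.0 | +0.70 | -0.80 | 59.1% | 98.4% |

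Worked row (b = 0.5, d = -0.5): residual SD = 2.8 × √0.75 = 2.425 and SE = 2.425 × √(2/60) = 0.443. Without a shift, 1.5 / 0.443 - 1.960 = 1.43 (92.3%). With it, 1.25 / 0.443 - 1.960 = 0.86 (80.6%). A simulation of 4,000 trials at these values averaged -1.23, against -1.25 from the formula.

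**4. Direction.** Disappointment in Arm 1 raises the control baseline; optimism in Arm 2 lowers the gabapentin baseline. Both make d negative, so a real benefit is understated. If gabapentin had no effect, the same negative d would make it look slightly harmful: at b = 0.5 and d = -0.5, the two-sided rejection rate is 8.7% instead of 5%.

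**5. Hypothesis 1.2.** The same algebra applies, with b replaced by the slope of opioid dose on baseline pain. The protocol gives no figure for it.

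**The case against.** The strongest reply is that the order is inferred. In section 1.6 the word that marks sequence links consent to randomisation only, and the sentence on questionnaires carries no time marker. Section 4.0 does not mention questionnaires. The calendars leave the order inside the Baseline column open, and section 5.6 mentions the medication record and demographic survey before the prescription. This stands: a reader might infer that the protocol fixes randomisation before the questionnaires, and it does not. It also does nothing to prevent that order, so the covariate is still unprotected.

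A reader might also infer from the section 5.6 timing sentence that baseline could be taken after radiation or drug has begun. Read alone, the sentence allows it. But the Baseline text opens by placing its activities before therapy, section 10.0 assumes a score from before radiation, and both calendars start gabapentin at Week 1. What is left is a wording mismatch with Appendix I. The missing VHNSS mark is the more substantial gap.

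There may be little room for a shift. Section 1.2 says that mucositis pain usually starts two to three weeks into chemoradiation, and the VHNSS asks about the past week, part of which may precede allocation. This is a fair reason to expect a small d. Pain from tumour or surgery still leaves some room.

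Finally, the bias can be checked, because an unadjusted week-six comparison does not use the baseline. That also stands, with two limits. At b = 0.5 it has 83.5% power against 92.3% for an adjusted analysis with a sound baseline, and it does not remove any effect of knowing the arm on the week-six ratings themselves.

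**Conclusion.** The point holds as a gap in protection, not as a demonstrated bias. Allocation is described directly after consent, no masking is described, nothing requires baseline self-report before the arm is known, and neither calendar schedules the VHNSS score that section 10.0 needs. The bias in the adjusted effect for Hypothesis 1.1 is -b × d. Over the assumed ranges with d negative it runs from +0.075 to +0.70 points (5% to 47% of the 1.5-point target). These figures rest wholly on assumed values, and the bias is zero if knowing the arm does not change reporting. The likely mechanisms would understate a real benefit, though the opposite sign cannot be excluded.

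Two wider inferences are not supported. A reader might extend the bias to Hypotheses 2.1 and 2.2 and Aim 4, since section 10.0 uses the covariate there as well. As worded in section 2.0, these relate pain to weight loss, PEG duration and general symptoms and state no contrast between arms, so there is no treatment effect to distort. A reader might also expect harm to change from baseline in mood, neurotoxicity and quality of life. Section 10.0 plans no such analysis and does not list these measures among its modelled outcomes.

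The change is worth making because it is nearly free and closes a route to bias in the main comparison.

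**What to change.** - In sections 1.6, 4.0 and 5.6, state one order: consent; all baseline self-report measures, including the VHNSS, together with the baseline pain-medication record; release of the assignment; then the Arm 2 prescription. Make completed baseline forms a condition for releasing the assignment.
- Add a Baseline mark for the VHNSS in both copies of the Appendix I calendar, so that the covariate in section 10.0 is collected before radiation and before allocation is known.
- Replace the timing sentence in section 5.6 with the Appendix I wording, "All baseline assessments must be done within 4 weeks before starting concurrent chemoradiation".
- Name an unadjusted week-six comparison of VHNSS pain as a sensitivity analysis for Hypothesis 1.1.

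Cost: a short wording amendment, one questionnaire that section 1.6 already lists (under 10 minutes by the protocol's own estimate), and slightly later randomisation for patients who have not finished their forms. Sample size, visits and treatment do not change.
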